11.4.2. Clinical Laboratory Tests

Subjects are required to fast for at least 8 hours prior to sample collection for laboratory testing at Visit 2E, Visit 4E, Visit 6E, Visit 8E, Visit 10E, Visit 12E, and Visit 14E (EOT/ET); fasting is also required at Week 6 (EOT) in the lead-in study of SEP-4199 CR, which serves as baseline (Visit 1E) in this long-term safety study. The clinical laboratory tests required by protocol are listed in Section 21, Appendix II.

Blood and urine samples will be collected for clinical laboratory tests. All clinical laboratory tests will be conducted centrally unless an exception is approved by the Medical Monitor. The site must notify the Medical Monitor as soon as possible when performing unscheduled laboratory tests.

Point of care (POC) testing will be used for the urine pregnancy test and rapid urine drug test. A serum pregnancy test should be submitted to the central lab for any positive urine pregnancy test, and a urine drug screen should be submitted to the central lab for any positive rapid urine drug test throughout the study.

For detailed instructions regarding clinical laboratory procedures, sampling, and shipping guidelines refer to the Central Laboratory Instructions Manual. Samples will be processed at a central laboratory to ensure consistency. All clinical laboratories will be College of American Pathologists (CAP) and Clinical Laboratory Improvement Amendments (CLIA) (or equivalent) certified.

11.4.3. Vital Signs

Blood pressure and pulse rate measurements will be taken in a supine and standing position. Blood pressure and pulse rate should first be taken with the subject in the supine position after resting for ≥ 5 minutes. Blood pressure and pulse rate will be taken again after standing for 2 to 4 minutes. The same arm should be used during each assessment of blood pressure and pulse rate throughout the study. If a subject develops symptoms consistent with orthostatic hypotension (light-headedness, dizziness, or changes in sensorium upon standing) at any point, his or her supine and standing blood pressure and pulse rate should be collected at that time in the manner described above.

Respiratory rate and temperature will also be measured, and all measurements will be recorded in the eCRF.

Weight will be measured in street clothes, without shoes and coat/jacket. BMI will be calculated in the analysis. Waist circumference will also be measured.

Vital signs will be obtained prior to clinical laboratory collection and performance of an ECG.

Clinically significant changes from signing the informed consent form (ICF) in vital sign parameters, as determined by the Investigator, will be noted as AEs in the eCRF.

11.4.4. Centrally-read ECG

All ECGs will be obtained in the supine position, after the subject has been resting supine for at least 10 minutes. ECGs will be 12-lead with a 10-second rhythm strip. ECGs should be obtained prior to drawing blood samples, with the exception of fasting blood draws. All attempts should be made to use the same ECG recorder for all visits within individual subjects. ECGs will be centrally read at a central facility, according to established quality assurance procedures for inter/intra reader variability. Refer to Section 20, Appendix I for additional information. ECG parameters to be collected include ventricular heart rate (beats/min), QT interval (msec), PR interval (msec), QRS interval (msec), RR interval (msec) and centrally-read overall ECG interpretation (Normal; Abnormal, insignificant; Abnormal, potentially significant; Abnormal, significant) including type of abnormality, if present. QTcF and QT interval corrected for heart rate using Bazett's formula (QTcB) will also be reported.

11.4.5. Neurological and Physical Examination

Complete physical examination as well as neurological examination will be performed. The physical examination includes an assessment of general appearance and a review of systems

(dermatologic, head, eyes, ears, nose, mouth/throat/neck, thyroid, lymph nodes, respiratory, cardiovascular, gastrointestinal, extremities, musculoskeletal, neurologic, and psychiatric systems). The neurological examination includes an assessment of general appearance, mental status, cranial nerves, motor system, sensory system, reflexes, coordination, and gait.

Any clinically significant changes from signing of the ICF, as determined by the Investigator, will be noted as AEs in the eCRF.

11.4.6. Safety Scales

11.4.6.1. Columbia-Suicide Severity Rating Scale (C-SSRS)

The C-SSRS is a tool designed to systematically assess and track suicidal AEs (suicidal behavior and suicidal ideation) throughout the study. The strength of this suicide classification system is in its ability to comprehensively identify suicidal events while limiting the over-identification of suicidal behavior. The C-SSRS will be administered by a trained rater at the site.

This study will utilize the "Since Last Visit" version of the C-SSRS.

Subjects who answer "yes" to "suicidal ideation" item 4 (active suicidal ideation with some intent to act, without specific plan) or item 5 (active suicidal ideation with specific plan and intent) on any post-Baseline C-SSRS assessment must be discontinued from the study, referred to the Investigator for follow-up evaluation, and followed until the event resolves; in addition, an associated AE must be reported.

Further information regarding administration of the C-SSRS, including rater training and certification as well as recording of C-SSRS scores, will be provided in the Study Reference Manual.

11.4.6.2. Young Mania Rating Scale (YMRS)

The YMRS will be administered as a safety assessment and to inform the identification of treatment-emergent mania or hypomania.

The YMRS is a clinician-rated 11-item instrument used to assess the severity of mania in subjects with a diagnosis of bipolar disorder. The 11 items assess: Elevated Mood, Increased Motor Activity/Energy, Sexual Interest, Sleep, Irritability, Speech (Rate and Amount), Language/Thought Disorder, Content, Disruptive-Aggressive Behavior, Appearance, and Insight. The YMRS will be administered by a qualified rater at the site. Further information regarding administration of the YMRS, including rater training and qualification as well as recording of YMRS scores, will be provided in the Study Reference Manual.

Treatment-emergent mania or hypomania is defined as a YMRS total score \geq 16 at any 2 consecutive post-Baseline visits or at the final visit, or an AE of mania or hypomania.

11.4.6.3. Abnormal Involuntary Movement Scale (AIMS)

The AIMS is a clinician-rated assessment of abnormal movements consisting of unobtrusive observation of the subject at rest (with shoes removed) and several questions for instructions directed toward the subject. Using a severity scale ranging from 0 (none) to 4 (severe), clinicians rate dyskinesia in several body regions including the facial area, extremities, and trunk. There are 2 items related to dental status, as well as 3 global impression items assessing overall severity,

incapacitation, and the subject's awareness of abnormal movements (Guy 1976, Munetz 1988). The AIMS raters will be required to meet specific credential and educational criteria before they are certified to rate for this study.

Further information regarding administration of the AIMS, including rater training and certification as well as recording of AIMS scores, will be provided in the Study Reference Manual.

11.4.6.4. Barnes Akathisia Rating Scale (BARS)

The BARS is a rating scale intended for the assessment of neuroleptic-induced akathisia. It consists of 4 items, including one item assessing objective restlessness, 2 items assessing subjective restlessness (awareness and related distress), and one global clinical assessment item. All items are anchored and utilize a 4-point scale, except for the global rating which uses a 6-point scale (from absence of akathisia through severe akathisia). The subjective and objective items are summed to yield a total score. The BARS can be administered in about 10 minutes (Barnes 1989, Barnes 2003, Schooler 2000).

Further information regarding administration of the BARS, including rater training and certification as well as recording of BARS scores, will be provided in the Study Reference Manual.

11.4.6.5. Modified Simpson-Angus Scale (SAS)

The modified SAS is a clinician-rated assessment of neuroleptic-induced Parkinsonism consisting of 10 items. Items are anchor-based, rated on a 5-point scale, and address rigidity, gait (bradykinesia), tremor, glabellar tap, and salivation (Simpson 1970).

Further information regarding administration of the modified SAS, including rater training and certification as well as recording SAS scores, will be provided in the Study Reference Manual.

11.4.6.6. Physician's Withdrawal Checklist (PWC)

Potential withdrawal effects will be assessed by the clinician using the PWC after completion of all scheduled effectiveness and safety assessments and procedures at Visit 14E (EOT/ET) and Follow-up (Visit 15E). The PWC is used to evaluate symptoms of withdrawal after discontinuation of study medication. Symptoms are assessed as present or absent; if present, then intensity is assessed as mild, moderate, or severe.

11.5. Pharmacokinetic Assessments

Blood samples will be collected for population pharmacokinetics and plasma prolactin at the following visits: Visit 2E (Week 2/Day 14), Visit 4E (Month 2), Visit 6E (Month 4), Visit 8E (Month 6), Visit 10E (Month 8), Visit 12E (Month 10), Visit 14E (Month 12), and Follow-up (Visit 15E, 7 ± 2 days after last dose). See Section 22, Appendix III for sample collection and handling guidelines.

Prior to PK blood sample collection, subjects will record the date and time of their 3 most-recent study drug doses; the clinical site staff will record the dates and times of the 3 doses in the eCRF for each of the PK collection visits during the treatment period.

Plasma samples will be analyzed for concentrations of aramisulpride and esamisulpride using a validated enantioselective liquid chromatography-tandem mass spectrometry (LC-MS/MS) method. Plasma samples will also be analyzed for prolactin concentrations by an enzyme-linked immunosorbent assay (ELISA).

Remaining plasma samples after amisulpride PK and prolactin analysis may also be used for the additional bioanalytical method development and/or characterization of putative metabolites of amisulpride and for other exploratory measurements, if needed.

11.6. Study Visits and Assessments

To ensure subject safety and data integrity, should circumstances warrant and with Sponsor approval, remote site/subject visits may be conducted.

11.6.1. Visit 1E: Baseline (Day -1)

The Open-Label Baseline visit of the present study is on the same day as Visit 6/EOT (Day 42) in the lead-in study of SEP-4199 CR. Subjects will be evaluated at this visit to determine their eligibility for the study. The following study-related procedures will be performed at Visit 1E; it is suggested that they be performed in the order presented below, as is possible by the site:

- Obtain informed consent, including signed informed consent for duplicate subject check (where local regulations allow).
- Review inclusion and exclusion criteria.
- Record subject demographics.
- Review concomitant medications. Medications taken during the lead-in study of SEP-4199 CR that are ongoing at the start of the current extension study will be entered into the eCRF.
- Record adverse events. Adverse events with onset during the lead-in study of SEP-4199 CR and ongoing at the start of the current extension study will be entered into the eCRF.
- Dispense study drug. Instruct the subject to administer study drug as a single oral dose in the morning at approximately the same time each day beginning the following day (Day 1).
- Schedule next visit:
 - Instruct subject to administer the morning dose prior to the clinic visit. Clinic visits are to begin no later than 6 hours postdose, if possible.
 - Instruct subject to record the date and time of last 3 doses prior to next visit and to bring back all used/unused study drug and packaging to the next visit.
- Schedule weekly telephone check-in with subject.

The following procedures conducted at Visit 6/EOT (Day 42) of the lead-in study of SEP-4199 CR do not need to be repeated for the Open-Label Baseline visit of this study:

• Physical and neurological examinations

- Vital sign measurements
- Weight
- Waist circumference
- 12-lead ECG
- Blood samples for the following laboratory tests (Subjects must have fasted for at least 8 hours.):
 - Hematology and Serum Chemistry
 - Thyroid Panel
 - Serum Prolactin
 - HbA1c
 - Lipid Panel
 - Serum Insulin
 - High-sensitivity C-Reactive Protein (hs-CRP)
- Blood sample for measurement of plasma concentrations of aramisulpride, esamisulpride, and prolactin.
- Urine sample for rapid urine drug test, urinalysis, and urine pregnancy test (human chorionic gonadotropin [β-hCG], female subjects of childbearing potential)
- MADRS
- HAM-A
- YMRS
- QIDS-SR16
- SDS
- EQ-5D-5L
- SHAPS
- CGI-BP-S
- C-SSRS
- AIMS
- BARS
- SAS

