4.3. Risk-Benefit Assessment

To date, one completed Phase 2 6-week clinical study (SEP380-201) evaluated fixed doses of SEP-4199 Immediate Release (IR) formulation at doses of 200 mg/day and 400 mg/day vs. placebo in subjects with bipolar I depression. In the full global intention-to-treat (ITT)

population, including North American, Latin American, European, and Japanese subjects (N = 337), both SEP-4199 IR 200 mg/day and 400 mg/day doses demonstrated significantly greater improvement compared to placebo (post-hoc adjusted p = 0.025 for both treatment groups using the same multiplicity adjustment approach as for the primary analysis). Based on the full global safety population, SEP-4199 IR was well tolerated in this study, with an overall adverse event (AE) rate (< 50%) in both dose groups that was comparable to that in the placebo group and a low rate (< 9% in either group) of discontinuations due to an AE. These results demonstrated proof of concept for the efficacy of SEP-4199 IR in the treatment of bipolar I depression and support further development of the SEP-4199 compound. However, safety and tolerability data for SEP-4199 IR in patients with bipolar I depression are currently limited to those collected over the 6-week treatment duration. Longer-term exposure to clinical doses of SEP-4199 is needed to fully evaluate safety, tolerability, and effectiveness.

A novel CR formulation of SEP-4199 has been developed. SEP-4199 CR was well tolerated in the PK and positron emission tomography (PET) imaging study in healthy volunteers (SEP380-105). Administration of SEP-4199 CR resulted in the same degree of dopamine D₂ receptor occupancy after multiple doses as did SEP-4199 IR at the same dosages, while exhibiting lower serum concentrations at C_{max}. The lower C_{max} of SEP-4199 CR was associated with substantially less QT interval corrected for heart rate (QTc) interval prolongation than was observed with SEP-4199 IR. Therefore, SEP-4199 CR is hypothesized to be therapeutically equivalent to SEP-4199 IR, but with an improved therapeutic index due to improved cardiac safety. For this reason, the SEP-4199 CR formulation will be evaluated in the current long-term open-label study.

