11.6.2. Visit 2E (Week 2/Day 14 [± 2 days])

The following study-related procedures will be performed at Visit 2E; it is suggested that they be performed in the order presented below, as is possible by the site:

- Administer MADRS.
- Administer YMRS.
- Administer CGI-BP-S.
- Administer C-SSRS.
- Administer AIMS.
- Administer BARS.
- Administer SAS.
- Review concomitant medications.
- Record adverse events.
- Obtain vital signs.
- Record weight.
- Collect blood sample(s) for the following clinical laboratory tests (Subjects must have fasted for at least 8 hours.).
 - Hematology and Serum Chemistry
 - Serum Prolactin
- Collect blood sample for measurement of plasma concentrations of aramisulpride, esamisulpride, and prolactin.
- Collect urine sample for urinalysis and rapid urine drug test.
- Perform 12-lead ECG.
- Perform study drug accountability.
 - Collect used/unused drug and packaging.
 - Confirm with the subject the date and time of their last 3 doses of study drug and record in the source and eCRF.
- Dispense study drug.
 - Instruct subject to dose once daily in the morning at approximately the same time each day at home.
- Schedule next visit:
 - Instruct subject to administer the morning dose prior to the clinic visit. Clinic visits are to begin no later than 6 hours postdose, if possible.

- Instruct subject to bring back all used/unused study drug and packaging to the next visit.
- Schedule weekly telephone check-in with subject.

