11.6.3. Visit 3E (Month 1/Day 30 [± 2 days])

The following study-related procedures will be performed at Visit 3E; it is suggested that they be performed in the order presented below, as is possible by the site:

- Administer MADRS.
- Administer YMRS.
- Administer CGI-BP-S.
- Administer C-SSRS.
- Review concomitant medications.
- Record adverse events.
- Obtain vital signs.
- Record weight.
- Perform 12-lead ECG.
- Collect urine sample for rapid urine drug screen and urine β-hCG (female subjects of childbearing potential).
- Perform study drug accountability.
 - Collect used/unused drug and packaging.
- Dispense study drug.
 - Instruct subject to dose once daily in the morning at approximately the same time each day at home.
- Schedule next visit:
 - Instruct subject to administer the morning dose prior to the clinic visit. Clinic visits are to begin no later than 6 hours postdose, if possible.
 - Instruct subject to record the date and time of last 3 doses prior to next visit and to bring back all used/unused study drug and packaging to the next visit.
- Schedule weekly telephone check-in with subject.

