11.6.4. Visit 4E (Month 2/Day 60 [± 5 days])

The following study-related procedures will be performed at Visit 4E; it is suggested that they be performed in the order presented below, as is possible by the site::

- Administer MADRS.
- Administer HAM-A.

- Administer YMRS.
- Administer CGI-BP-S.
- Administer QIDS-SR16.
- Administer SDS.
- Administer EQ-5D-5L.
- Administer SHAPS.
- Administer C-SSRS.
- Administer AIMS.
- Administer BARS.
- Administer SAS.
- Review concomitant medications.
- Record adverse events.
- Obtain vital signs.
- Record weight.
- Collect blood sample(s) for the following clinical laboratory tests (Subjects must have fasted for at least 8 hours.).
 - Hematology and Serum Chemistry
 - Serum Prolactin
 - HbA1c
 - Lipid Panel
 - Serum Insulin
 - Thyroid Panel
- Collect blood sample for measurement of plasma concentrations of aramisulpride, esamisulpride, and prolactin.
- Collect urine sample for rapid urine drug test, urinalysis, and urine β-hCG (female subjects of childbearing potential).
- Perform 12-lead ECG.
- Perform study drug accountability.
 - Collect used/unused drug and packaging.
 - Confirm with the subject the date and time of their last 3 doses of study drug and record in the source and eCRF.
- Dispense study drug.

- Instruct subject to dose once daily in the morning at approximately the same time each day at home.
- Schedule next visit:
 - Instruct subject to administer the morning dose prior to the clinic visit. Clinic visits are to begin no later than 6 hours postdose, if possible.
 - Instruct subject to bring back all used/unused study drug and packaging to the next visit.
- Schedule weekly telephone check-in with subject.

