## 18.3. ECG EVALUATIONS

Data from the centrally over-read ECG (Electrocardiogram) results will be included in the reporting of this study.

The following ECG parameters will be reported for this study:

- PR Interval (msec)
- RR Interval (msec)
- QRS Duration (msec)
- QRS Axis (deg)
- QT Interval (msec)
- QTcF Interval (msec) (Fridericia's Correction of QT interval)
- QTcB Interval (msec) (Bazett's Correction of QT interval)

- Heart Rate (bpm)
- Overall assessment of ECG as determined by the central over-read:
  - Normal
  - Abnormal, Insignificant
  - Abnormal, Potentially Significant
  - Abnormal, Significant
  - Exclusion Alert (only given for the Screening visit of core study). In table summaries, the category of "Exclusion Alert" will be combined into the category of "Abnormal, Significant".
  - Not Evaluable
- ECG findings

ECG findings will only be listed. Other ECG data will be summarized in tables as well as presented in listings.

The following summaries will be provided:

- For quantitative measurements: By-visit summary of observed values at DB Baseline, OL Baseline, each scheduled OLE study visit (starting from Visit 2E, Visit 1EJ for Japan subjects), and LOCF; by-visit summary of change from DB Baseline at each scheduled OLE study visit (starting from Visit 1E) and LOCF; by-visit summary of change from OL Baseline at each scheduled post-OL Baseline extension study visit (starting from Visit 2E, Visit 1EJ for Japan subjects) and LOCF.
- For ECG overall assessment results as determined by the central over-read ("Normal", "Abnormal, not Clinically Significant (NCS)", "Abnormal, Clinically Significant (CS)", "Not Evaluable"): By-visit summary of number and percentage of subjects in each category at DB Baseline, OL Baseline, each scheduled OLE study visit (starting from Visit 2E, Visit 1EJ for Japan subjects), and LOCF.
- Shift in ECG overall assessment as determined by the central over-read from DB Baseline to each scheduled OLE study visit (starting from Visit 1E) and LOCF, and shift from OL Baseline to each post-OL Baseline extension study visit (starting from Visit 2E, Visit 1EJ for Japan subjects) and LOCF.
- Number and percentage of subjects who met each of the QTc interval prolongation criteria (see [Section 18.3.1](#)) considering both DB Baseline and OL Baseline. The period of evaluation includes both the OLE treatment period and the OLE follow-up period up to and including 7 days post the last OLE dose, including unscheduled visits.

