## 19. PHARMACOKINETIC ANALYSIS

All PK analysis will be performed using Safety population.

Blood sample for plasma concentrations of R-amisulpride, S-amisulpride, total amisulpride, and/or plasma prolactin measurement will be collected at: Visit 1E (coinciding with Visit 9 of SEP380-301), Visit 2E, Visit 4E, Visit 6E, Visit 8E, Visit 10E, Visit 12E, Visit 14E, and Visit 15E/Follow-up. Any plasma concentration or summary statistics below the lower limit of quantification (LLOQ) will be represented by "BLQ" (below the limit of quantification) in tables and listings. Amisulpride plasma concentration will not

be presented for the placebo group.

R-amisulpride, S-amisulpride, total amisulpride, and plasma prolactin concentrations at each scheduled sample collection time point (including ET and Follow-up, see [Section 7.4](#) for mapping of the ET visit) will be summarized descriptively (n, mean, median, minimum, maximum, coefficient of variation [CV] and if appropriate, geometric mean and geometric CV [GCV]). In addition, if there is at least 1 concentration < LLOQ within a treatment group at a time point, it will be set to  $\frac{1}{2}$  LLOQ for summary statistics calculations. Number and percentage of concentrations that are below the LLOQ will be provided for each visit. All PK summaries will be presented.

Population PK analysis methods will be used to characterize the PK/PD profiles in subjects treated with SEP-4199 CR. Analysis methods and results of population PK and PD analysis will be described in a separate document from the SAP and clinical study report.

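### The SAP 19 concentration tables take no account of time since last dose and count early-termination samples taken up to 7 days off drug as on-treatment visits

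*Protocol*

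**What the plan says.** **Timing in the clinic.** Protocol 11.6.1 to 11.6.13 tell the subject to dose before coming in, and add: "Clinic visits are to begin no later than 6 hours postdose, if possible". This limits when the visit starts and is not firm. Protocol Appendix III requires the PK sample to follow that day's dose and its actual time to be recorded, but sets no window. The order of procedures is advisory: "it is suggested that they be performed in the order presented below, as is possible by the site".

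**What is recorded.** Under Protocol 11.5, "the clinical site staff will record the dates and times of the 3 doses in the eCRF for each of the PK collection visits" during treatment. These visits are 2E, 4E, 6E, 8E, 10E, 12E and 14E. Section 11.6.14 collects the same information at Visit 14E, which doubles as the early-termination visit.

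**What is analysed.** SAP 19 summarises "R-amisulpride, S-amisulpride, total amisulpride, and plasma prolactin concentrations at each scheduled sample collection time point", including early termination and follow-up, and points to SAP 7.4 for placing the early-termination visit. SAP 7.4 assigns early-termination measurements taken within 7 days of the last dose to the next visit at which that assessment was due. SAP 18.3 gives a "by-visit summary of change from OL Baseline at each scheduled post-OL Baseline extension study visit" for ECG parameters. The recorded times of the last three doses appear in the SAP only in a footnote to the schedule (Appendix 7).

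**The concern.** A concentration means little without the time since the dose that produced it. Two features blur the by-visit tables.

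- **Same-day samples** can come from any time after the morning dose, with no firm upper limit.
- **Early-termination samples** may come from subjects who stopped drug days before. These enter a column labelled, for example, OL Month 4, although they describe washout. The effect on means and coefficients of variation (CVs) has one direction: levels look lower and more variable than they were on drug. Plasma prolactin, summarised in the same way, is exposed to the same mixing.

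The protocol itself gives a reason to care about timing for QTc. Section 4.3 says that the lower peak concentration of the CR formulation "was associated with substantially less QT interval corrected for heart rate (QTc) interval prolongation than was observed with SEP-4199 IR". By-visit QTc means carry no time since dose either, and the SAP 7.4 mapping covers safety data too.

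**Working it through.** The plan states no figure of its own here, so there is none to reproduce.

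**1. How far off drug can a mapped sample be?** SAP 7.4 allows up to 7 days. The follow-up visit is at 7 ± 2 days, that is days 5 to 9 after the last dose. The two ranges overlap on days 5 to 7. In that overlap a Visit 15E sample is reported under Follow-up, while an early-termination sample at the same distance from the last dose is reported under an on-treatment month.

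**2. How much drug is left?** The documents give no half-life, so 8, 12 and 24 h are assumptions. With simple exponential decline, the fraction left after d further days is f = 2^(−24d / half-life).

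| Half-life (assumed) | d = 1 | d = 7 |
|---|---|---|
| 8 h | 2^(−3) = 12.5% | < 0.01% |
| 12 h | 2^(−2) = 25% | about 0.01% |
| 24 h | 2^(−1) = 50% | 2^(−7) = 0.78% |

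Slow absorption from a CR tablet would leave somewhat more at one day.

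**3. What does one such sample do to a visit summary?** Take n samples, all at the same level except one at fraction f. The arithmetic mean falls by (1 − f)/n, and the geometric mean is multiplied by f^(1/n). SAP 4.4 gives 64 enrolled, so n = 64 is the most any visit can have, and it gives the smallest effect.

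| f | Fall in mean, n = 64 | Fall in geometric mean, n = 64 |
|---|---|---|
| 0.50 | 0.5/64 = 0.8% | 1 − 0.5^(1/64) = 1.1% |
| 0.125 | 0.875/64 = 1.4% | 1 − 0.125^(1/64) = 3.2% |
| 0.0078 | 0.992/64 = 1.6% | 1 − 0.0078^(1/64) = 7.3% |

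One sample also adds spread. The variance it contributes is (1 − f)²/n. At f = 0.0078 the SD is 0.992/8 = 0.124 and the mean 0.984, a CV of 12.6% from that sample alone. Effects grow as n falls with dropout or by treatment column, and with each further mapped sample.

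**4. Can time since dose be derived?** At the seven on-treatment PK visits, yes, from the recorded dose and sample times. At the six ECG-only visits (3E, 5E, 7E, 9E, 11E, 13E) the protocol does not require the last three dose times, so an ECG there cannot be placed reliably.

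**5. How much does the order of procedures matter?** In the listed order, blood follows 7 scales at 2E, 12 at 4E to 12E and 13 at 14E. (Protocol 11.4.6.6 puts the PWC after everything else, which would make 12 at 14E.) The ECG follows 4 to 13.

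The documents give about 10 min for BARS, 1–2 min for CGI-BP-S, and 7–9 min for vital signs (5 supine plus 2–4 standing). Assume 3–15 min for each other scale. At 4E the time before the draw is then 10×3 + 10 + 1 + 7 = 48 min to 10×15 + 10 + 2 + 9 = 171 min. A visit starting at 6 h has its draw at 6.8 to 8.85 h.

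To size a delay, assume a one-compartment steady-state model with a 24 h interval, half-life 8–24 h and absorption rate 0.15–0.6 per hour. Eight more scales (12 − 4) at an assumed 5–15 min each is 40–120 min. From 6.5 h, such a delay changes concentration by about +1% to −14%. The modelled peak lies between 3.5 and 8.1 h.

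**The case against.** The strongest reply is that these samples are collected for population PK. That analysis is planned in a separate document (Protocol 15.4.4, SAP 19), can use the actual dose and sample times, and benefits from varied sampling times. This stands for the model-based objectives. It does not repair the descriptive tables that SAP 19 itself specifies.

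Appendix III requires a same-day dose before sampling, so ordinary visits should not yield off-drug samples. This also stands. The route that remains is the early-termination mapping, where a subject may already have stopped drug.

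For QTc, SAP 18.3 and 18.3.1 count subjects who meet prolongation criteria at any post-baseline time point, against both baselines and with a listing. Those counts do not rest on by-visit means.

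Time bands will be thin with 64 subjects, and the SAP has already dropped subgroups because of size. That argues for pooling over visits, as proposed below.

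A reader might infer that the scales push the ECG past the peak and so understate QTc effects. The documents do not support this. The order is only suggested, no time of peak or half-life is given, and on the assumed grid a later ECG could be nearer the peak or further from it. The Section 4.3 statement compares formulations and says nothing about when CR peaks.

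**Conclusion.** The point holds for the SAP 19 concentration summaries: they ignore recorded time since dose, and by rule they admit off-drug early-termination samples to on-treatment visits. At n = 64, one seven-day sample costs at least about 1.6% of an arithmetic mean and 7% of a geometric mean. One-day samples cost about 1 to 3% of a geometric mean, with more at smaller visits. These sizes rest on the assumed half-life of 8–24 h, simple exponential decline and otherwise equal levels. The number of early-termination samples taken off drug is not given. SAP 4.4 links the 64 enrolled to early termination of the lead-in study and SAP 4.7 refers to study early termination, so such visits may not be rare.

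For QTc the point is weaker. By-visit means lack time since dose, but outlier counts are planned and no understatement is shown. A reader might also infer that sampling times are uncontrolled, or that the visit should be reordered. Sampling is tied to that morning's dose and to a soft start limit, and reordering is largely moot now that enrolment has ended at 64. All analyses are descriptive, so no test or sample size is affected.

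**What to change.** **SAP 19**
1. Derive time since last dose for each PK sample from the recorded dose and sample times.
2. Exclude samples with no same-day dose, including early-termination samples mapped under SAP 7.4, from the on-treatment visit summaries, and show them separately.
3. List every concentration with its time since dose.
4. Add one table of concentrations by time band, pooled across visits.

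**SAP 18.3**
1. Add time since dose to the QTc listing.
2. Give one pooled summary of QTcF change by time band for the PK visits.
3. State that the six ECG-only visits require no record of the last three dose times and are therefore not in that table.

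**Cost.** One derived variable, a few table rows and two listing columns, all from data already collected at PK visits. The time bands will be small and should be read as description only.
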